PART B STUDY DESCRIPTION

TITLE OF PROTOCOL	Development of a two-stage cervical cancer screening algorithm for Botswana
Principal Investigator	[name]

B1. PURPOSE OF PROTOCOL

Cervical cancer screening programs vary across settings and there is no clear guidance for effective screening programs for HIV-positive women. Evaluating the performance of algorithms that include human papillomavirus (HPV) DNA testing as first stage screening in high HIV prevalence settings like Botswana is essential for establishing an evidence-based strategy for cervical cancer screening in HIV-positive women. The proposed study seeks to evaluate sensitivity, specificity, and positive predictive value (PPV) of two different two-stage cervical cancer screening algorithms for HIV-positive women in Botswana: HPV followed by Papanicolaou (Pap) smear, and HPV followed by visual inspection with acetic acid (VIA). The specific aims are:

1. To determine the sensitivity, specificity, and PPV of a two-stage screening algorithm that utilizes HPV testing followed by Pap smear for the detection of high-grade cervical dysplasia, using colposcopy with histology as the gold standard.
2. To determine the sensitivity, specificity, and PPV of a two-stage screening algorithm that utilizes HPV testing followed by VIA for the detection of high-grade cervical dysplasia, using colposcopy with histology as the gold standard.

B2. SIGNIFICANCE AND BACKGROUND FOR THE STUDY

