Botswana's screening strategy is similar to low-resource countries in the region. Given logistical and implementation challenges associated with a pathology-dependent screening test,^{xliiv} a screen-and-treat approach with VIA was introduced in Botswana in 2011.^{xliv} Currently the standard of care in Botswana is for women to be screened either with a Pap smear or VIA alone. If she has an abnormal Pap smear result, she is referred for colposcopy; if she has an abnormal VIA result she is either offered cryotherapy or a loop electrosurgical excision procedure, depending on the size of the lesion. In developed countries, screening protocols have incorporated HPV DNA testing as it has a higher sensitivity in detecting women at risk of developing cervical cancer. Botswana plans to roll out HPV DNA testing as it has unique resources that allow for a more resource-intensive and effective strategy. However, because HPV DNA testing is sensitive but not specific, HPV testing alone would result in overtreatment of women who are unlikely to develop cervical cancer. Fortunately, pathology services have improved dramatically since 2011, and Pap smear may be an appropriate follow-up after a positive HPV test. VIA is also becoming more available nationally. An efficient, high-impact, two-stage strategy with primary HPV testing followed by either Pap or VIA can now be introduced nationally to reduce overtreatment and potential harm to women. Comparing these two strategies will provide essential data to inform national cervical cancer screening policy in Botswana and the surrounding region.

B3. DESCRIPTION OF RESEARCH PROTOCOL**A. Study Design – Overview, Methods, Procedures*****Study Population and HPV Screening***

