The proposed study will enroll 300 women for HPV testing in order to evaluate 81 HPV-positive women (see Sample Size calculations below). The first 100 enrollments will be nested within an existing cross-sectional pilot study designed to determine the uptake, acceptability, and feasibility of testing women for HPV using self-collected samples. The goal of this 100-person pilot study is to inform the future scale-up of primary HPV screening, by answering the question of whether self-collected swabs are as good as provider-collected swabs. These 100 participants will self-collect a vaginal specimen and undergo a concomitant provider-collected specimen for HPV testing; a provider-collected approach will be used for the subsequent 200 women who enroll for this proposed study. Co-enrollment with the existing pilot study leverages the existing study and facilitates use of the same staff and resources to ultimately accrue 300 women at minimal cost.

Research question

Which two-stage cervical cancer screening algorithm is more effective for HIV-positive women in Botswana: HPV followed by Papanicolaou (Pap) smear or HPV followed by visual inspection with acetic acid (VIA)?

Study Procedures

[figure not shown]
For all 300 participants, HPV testing will be performed with either the commercially-available Cepheid Xpert[®] HPV Assay or the commercially-available Roche Cobas[®] HPV Assay for provider- and participant-collected samples, as per the protocol of the HPV pilot study. The pilot study currently utilizes a Cepheid GeneXpert machine on loan from the National Health Laboratory (NHL), and the duration of its availability is unknown. Should the GeneXpert machine become unavailable, the Roche Cobas[®] machine at the NHL will be used for HPV testing. After the HPV pilot study ends, the remaining 200 participants will be enrolled and screened in a similar manner using a provider-collected approach. This study introduces Pap smear collection for all participants at the time of provider-collected HPV specimen. Pap smear will be prepared using standard technique at the site of collection.

Participants who test HPV-negative will have their Pap smear sent to the NHL for staining and pathologist evaluation. If the Pap smear is abnormal, they will be referred to colposcopy per current Botswana Cervical Cancer guidelines.

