Per the protocol of the HPV pilot study, participants who test HPV-positive will be asked to return for colposcopy and will undergo further diagnosis and treatment for cervical cancer per national guidelines. Participants who have positive HPV screening will have: 1) Pap smear sent to the NHL for review and 2) VIA at the colposcopy visit but performed prior to colposcopy. At the second visit - prior to the colposcopy - a trained nurse will conduct VIA using the Botswana standard protocol. After application of acetic acid to the cervix, the nurse will record visual results as positive or negative. If VIA is positive based on assessment of the lesion(s), the nurse will record a recommendation for either cryotherapy or loop electrosurgical excision procedure (LEEP). Since all of these HPV-positive participants will undergo colposcopy, the participants will not be informed of the VIA results, as neither cryotherapy nor LEEP will be administered based on the VIA results. Rather, the participants will proceed to colposcopy as planned in the HPV pilot study (and as will be continued for the women participating only in this study) and results of colposcopy will determine further diagnosis and treatment. This design leverages the existing HPV pilot study and enables us to assess the utility of both HPV/Pap and HPV/VIA two-stage algorithms while providing the highest-quality follow-up to cervical cancer screening abnormalities in Botswana.

Participants will thus have a total of two study-related encounters if they are HPV positive - one for initial screening and the one for the second-stage of screening and colposcopy. Participants who are HPV negative will only have the one study-related initial screening visit. Participants will also be asked if they want to be contacted in the future regarding participation in future research related to cervical screening and treatment. If the participant agrees, they will check yes for future contact in the consent form.

Cervical cancer screening study flow

The study site is only in Botswana; however, statistical analysis will be done with support from staff at BIDMC.

A detailed data monitoring and safety plan has been developed. All adverse events will be reviewed by the PI and co-investigators. All serious adverse events will be reviewed by the PI, co-investigators and a designated safety monitor, [name].

B. Statistical Considerations

Sample Size

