The goal of a two-stage algorithm is to increase PPV while maintaining sensitivity and specificity, and thus reduce overtreatment. Sample size assumptions were based on preliminary data, existing literature, and patient behavior regarding clinical follow-up. Among the first 25 women recruited in the parent study, the incidence of HPV-positivity was 30%. In a population with relatively high HIV prevalence, the PPV of an HPV-positive test for high-grade cervical dysplasia was 24%.^{xlvi} Our sample size calculation was targeted to detect an improvement in PPV of 25% between HPV testing alone and either two-stage algorithm (a PPV of 49% for the two-stage algorithms). Assuming a two-sided test and an alpha of 0.05, a sample size of 81 participants will yield over 80% power to detect the specified difference. Clients receiving care at the Infectious Disease Care Clinic (IDCC) tend to return for clinical follow-up appointments, because they come to IDCC each month to obtain their free anti-retroviral medications. Clients seeking care at the gynecology outpatient clinic may be less integrated into routine care. Thus, we anticipate that approximately 10% of HPV-positive participants will not return for colposcopy. The proposed study will aim to enroll 300 participants to yield 90 who are HPV positive 81 of whom we expect to return for colposcopy.

Data analysis

All data will be analyzed using SAS 9.4 (Cary, NC) at Beth Israel Deaconess Medical Center. Descriptive statistics will be presented as mean with standard deviation, median with interquartile range, or proportion, based on data type and distribution. Data will be compared using the appropriate parametric or non-parametric test for continuous variables and Chi-square or Fisher's exact test for categorical variables. All tests will be two-sided and a p-value <0.05 will be considered statistically significant.

We will calculate sensitivity, specificity and PPV of HPV/Pap smear and HPV/VIA to detect high-grade cervical dysplasia amongst HPV-positive participants. We will also evaluate associations between HPV type, cytology, VIA result, and histopathology results.

C. Subject Selection

Inclusion and Exclusion Criteria

Inclusion criteria for the study are:

- 1) ≥ 25 years of age
- 2) HIV-positive
- 3) Competent to understand study procedures and give informed consent.

Exclusion criteria are:

- 1) Currently pregnant (as diagnostic procedures for cervical cancer are often deferred during pregnancy)

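### The research question asks which algorithm is more effective, but the analysis plans no paired Pap-versus-VIA difference and no interval

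*Combined protocol and SAP*

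**What the plan says.** The research question in B3.A is comparative: "Which two-stage cervical cancer screening algorithm is more effective for HIV-positive women in Botswana", with HPV/Pap and HPV/VIA as the two candidates. Section B2 gives the same purpose: "Comparing these two strategies will provide essential data to inform national cervical cancer screening policy in Botswana and the surrounding region".

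The design is paired. Under Study Procedures in B3.A, "Participants who have positive HPV screening will have: 1) Pap smear sent to the NHL for review and 2) VIA at the colposcopy visit", performed before the colposcopy itself. Both tests are judged against one reference, "Since all of these HPV-positive participants will undergo colposcopy". The paired set is therefore the HPV-positive women who return.

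The aims in B1 are separate, one per algorithm. The first reads "To determine the sensitivity, specificity, and PPV of a two-stage screening algorithm that utilizes HPV testing followed by Pap smear", and the second does the same for VIA. The data analysis text in B3.B follows the aims: "We will calculate sensitivity, specificity and PPV of HPV/Pap smear and HPV/VIA to detect high-grade cervical dysplasia amongst HPV-positive participants". It adds: "We will also evaluate associations between HPV type, cytology, VIA result, and histopathology results". A general sentence names chi-square or Fisher's exact test for categorical variables, without assigning them to any contrast. The sample size addresses HPV testing alone (PPV 24%) against either two-stage algorithm (PPV 49%).

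**The concern.** No sentence in the plan states a difference in accuracy between Pap and VIA, an interval for one, or a paired method. The associations sentence would relate each test to histology, or the tests to each other; neither is a difference in accuracy. The sample size concerns another contrast. The gap is against the research question and the policy rationale, not against the aims.

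Followed as written, the plan sets two columns of point estimates side by side, and nothing shows whether a gap between them exceeds chance. With about 19 diseased women a gap of two women is already about 10 points of sensitivity, and the result is meant to guide national policy. A secondary, conditional harm arises if the general chi-square/Fisher sentence is applied to Pap versus VIA, because those tests treat the same women as two independent groups.

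**Working it through.** **1. The plan's own figure.** Enrolment: 300 × 0.30 = 90 HPV-positive; 90 × 0.90 = 81 at colposcopy. The plan names no power formula. Treating 24% versus 49% as two independent groups of 81, with mean proportion 0.365:

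- null SE = √(2 × 0.365 × 0.635 / 81) = 0.0757
- alternative SE = √((0.24 × 0.76 + 0.49 × 0.51) / 81) = 0.0731
- power = Φ((0.25 − 1.96 × 0.0757) / 0.0731) = 91.8%

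This agrees with the stated power of over 80%, but for HPV alone versus an algorithm, not Pap versus VIA.

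**2. Size of the paired sets.** 81 × 0.24 = 19.4, so about 19 women with high-grade dysplasia and 62 without.

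**3. Assumptions.** The documents give no triage accuracies for this population and no correlation between the tests. All accuracies below are assumed, and the within-woman (phi) correlation is taken as 0, 0.1, 0.3 and 0.5, the same in cases and non-cases. Simulated figures use 200,000 multinomial replicates per setting; for PPV, n = 81 and the number of cases is Binomial(81, 0.24).

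**4. Plan as written, with identical algorithms.** Chance that the two point estimates differ by 10 points or more:

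- sensitivity (true value 70% or 80%): 37-59%
- specificity among HPV-positive women (77.5% or 80%): 4-16%
- PPV (49%, with sensitivity 60% or 80%): about 10-38%

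Hand check for sensitivity 70%, correlation 0: the discordant proportion is 2 × 0.7 × 0.3 = 0.42, and the SD of the net count is √(19 × 0.42) = 2.82. A net 2 or more of 19 women has probability about 2 × [1 − Φ(1.5 / 2.82)] = 0.60, against 59% simulated.

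**5. What a paired interval would show.** With accuracies p₁ and p₂ and correlation φ, both tests are correct with probability P = p₁p₂ + φ√(p₁(1−p₁)p₂(1−p₂)). The discordant proportions are b = p₁ − P and c = p₂ − P, and the 95% half-width is 1.96 × √((b + c − (b − c)²) / n).

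Example, sensitivity 80% versus 60%, φ = 0: P = 0.48, b = 0.32, c = 0.12, giving 1.96 × √((0.44 − 0.04) / 19) = 28 points.

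PPV follows from sensitivity, specificity and 24% prevalence; for example 0.8 × 0.24 / (0.8 × 0.24 + 0.15 × 0.76) = 63%. Its half-width is 1.96 × the SD of the simulated difference.

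| Contrast (half-width, points) | φ = 0 | 0.1 | 0.3 | 0.5 |
|---|---|---|---|---|
| Sensitivity 80% vs 60%, n = 19 | 28 | 27 | 24 | 20 |
| Specificity 85% vs 70%, n = 62 | 14.5 | 13.7 | 12.2 | 10.4 |
| PPV 63% vs 46% (sensitivity 80% both) | 18.8 | 17.9 | 16.0 | 13.8 |
| PPV 56% vs 46% (sensitivity 60% vs 80%) | 20.9 | 19.9 | 17.9 | 15.5 |

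The PPV rows use specificities of 85% and 70%. Treating the two PPVs as independent would give about 25 and 27 points.

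**6. Only if chi-square were used for Pap versus VIA.** Power in percent, for φ = 0, 0.1, 0.3, 0.5:

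| Contrast | Chi-square | Paired test |
|---|---|---|
| PPV 63% vs 46% | 17, 16, 13, 10 | generalised score: 43, 47, 57, 72 |
| PPV 56% vs 46% | 5, 4, 3, 2 | generalised score: 17, 18, 21, 25 |
| Specificity 85% vs 70% | 51-52 throughout | McNemar score: 53, 57, 67, 81 |
| Sensitivity 80% vs 60% | 28, 27, 24, 20 | McNemar score: 24, 26, 33, 46; exact: 15, 16, 17, 17 |

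With equal PPVs of 49%, chi-square rejects in at most 0.5% (sensitivity 80%) or 1.3% (sensitivity 60%) of studies instead of 5%; the score test rejects in 4.9-5.2%.

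**The case against.** The strongest reply is that the analysis delivers exactly what the two aims ask for, so the mismatch is with one research-question sentence and one background sentence. That is correct and limits the point: the aims can be met as planned. But a reader of B2 and B3.A will expect a comparison.

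A second reply is that the general sentence on comparing data foresees some testing. It names no Pap-versus-VIA contrast, and its categorical tests do not fit paired data. The chi-square harm remains hypothetical and its size is mixed: at low correlation chi-square has slightly more power than McNemar for sensitivity, and for specificity the loss is small unless correlation exceeds about 0.1. In the unequal-sensitivity PPV case neither test is useful.

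Third, only 81, 24% and 49% come from the plan; the accuracies, correlations and 10-point threshold are chosen. That stands, which is why ranges are shown. The wide ranges in B2 (cytology sensitivity 43-94%, VIA 17-100%) are for stand-alone tests, not triage of HPV-positive women. Chance gaps are frequent mainly for sensitivity, less so for specificity.

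Finally, the data analysis text sets no threshold for a positive Pap, and B5 provides biopsy only where lesions are abnormal, so a Pap-VIA difference depends on definitions still to be written. That is true, but the separate estimates already planned depend on them equally. Since both results are collected, a paired analysis also remains possible later, though it would not then be pre-specified.

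**Conclusion.** The concern holds. The stated research question has no planned inferential answer, although the design supplies the paired data to give one. On the plan's figures of about 19 cases and 62 non-cases, identical algorithms would appear 10 or more points apart in roughly 37-59% of studies for sensitivity, and less often for PPV and specificity. These sizes rest on assumed accuracies and correlations of 0 to 0.5; the absence of a stated contrast and interval does not. The comparison is not powered: an interval would mostly show how little can be concluded about sensitivity. This should be fixed before the data are analysed, but it does not prevent the two aims from being met.

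**What to change.** Add to the data analysis section wording such as:

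> Among HPV-positive women with Pap, VIA and reference results, we will estimate the HPV/Pap minus HPV/VIA difference in sensitivity (women with high-grade dysplasia), specificity (women without) and PPV, each with a 95% confidence interval and the woman as the unit of analysis. This comparison is estimation and is not powered; a non-significant difference will not be read as equivalence.

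- **Intervals:** for example, a paired interval for sensitivity and specificity and a bootstrap by woman for PPV. The choice of paired interval is not critical: in simulation the simple paired Wald interval covered 93-97% at n = 19, all paired intervals tried covered 94-97% at n = 62, and the percentile bootstrap for PPV covered 94-96%.
- **P-values, if reported:** McNemar for sensitivity and specificity and a generalised score test for PPV. Keep chi-square and Fisher's exact for independent groups.
- **Scope:** say that the associations analysis is separate from this contrast. State the Pap threshold and how women without a biopsy are classified, since each algorithm's own estimates need these too.
- **Alternative:** if no comparison is intended, reword the research question to match the two aims.

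The cost is plan wording and a few lines of SAS code, with no extra women or visits. The downside is that wide intervals become explicit, about ±20 to 28 points for sensitivity and ±14 to 21 for PPV under the assumed values, so the contrast will seldom settle sensitivity.

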3) Colposcopy: Current standard of care in Botswana for patients with Pap smear results of high grade or persistent low grade are referred for colposcopy. Based on this standard of care, we are referring all patients with positive HPV results to colposcopy. Colposcopy allows for evaluation of the cervix under a microscope to detect any abnormal lesions. Patients with abnormal lesions will undergo biopsy as indicated in routine colposcopy procedure. Though colposcopy can be uncomfortable, it is a routine step in cervical cancer screening, as follow-up for abnormal results, and the benefit of diagnosing cervical cancer or pre-invasive cervical disease outweigh the risk of the procedure.

4) Loss of confidentiality: To protect patient privacy, all data will be handled in a confidential manner. Moreover, participants will be assigned a unique study identification number. The analytic dataset will only contain de-identified data.

Minimizing/alleviating risk:

Informed consent and strict confidentiality will be rigorously enforced to minimize risks to participants and their partners. All study personnel will receive training in the informed consent process.

Participants will be provided with a phone number whereby a member of the clinic staff and the Principal Investigators, [name] and [name], may be contacted to answer questions or in case of emergency, psychological distress or any questions regarding their informed consent.

Risk/Benefit Ratio:

Any woman seeking cervical cancer screening in Botswana will require a pelvic exam for any available screening modality currently available in Botswana (Pap and VIA), and thus provider-collected HPV testing does not introduce a new discomfort. The benefits to the participants of more sensitive diagnosis of pre-invasive cervical disease with HPV testing outweigh the discomfort of sample collection.

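### Does the Aim 1 analysis fail because the protocol names no cytology cut-off for a positive Pap and words the Botswana Pap standard in two ways?

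*Combined protocol and SAP*

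**What the plan says.** Aim 1 (B1) asks for the sensitivity, specificity and PPV of HPV testing followed by Pap smear, and Data analysis (B3.B) repeats this: "We will calculate sensitivity, specificity and PPV of HPV/Pap smear and HPV/VIA to detect high-grade cervical dysplasia amongst HPV-positive participants". Neither names a cytology grade. For HPV-positive women, B3.A only has the smear sent to the national laboratory for review, whereas the nurse records VIA as positive or negative.

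The Pap standard is worded in two ways:

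- B2 introduces current practice with "Currently the standard of care in Botswana is for women to be screened either with a Pap smear or VIA alone" and continues "If she has an abnormal Pap smear result, she is referred for colposcopy".
- B3.A, on HPV-negative women, uses the same word and points to the national guideline: "If the Pap smear is abnormal, they will be referred to colposcopy per current Botswana Cervical Cancer guidelines".
- B5, under the risks of colposcopy, says: "Current standard of care in Botswana for patients with Pap smear results of high grade or persistent low grade are referred for colposcopy".

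On the number of smears, B3.A says: "This study introduces Pap smear collection for all participants at the time of provider-collected HPV specimen". On visits it says: "Participants will thus have a total of two study-related encounters if they are HPV positive", the second being for VIA and colposcopy, and "Participants who are HPV negative will only have the one study-related initial screening visit". No repeat smear and no collection of past cytology is described.

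**The concern.** Sensitivity, specificity and PPV each need a yes/no Pap result. VIA has one by design and cytology does not. The natural fallback, local practice, splits on the low-grade smear. Under the wording of B2 and B3.A that smear is positive. Under B5 it depends on persistence, which a single smear cannot show, so an analyst following B5 could count only high-grade smears.

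The two analysts would describe two different algorithms. Sample Size (B3.B) frames the gain as PPV rising from 24% to 49%, and the research question sets Pap against VIA. If low-grade smears were numerous, the choice of cut-off could move either answer, and a cut-off chosen after histology is known could be chosen to suit.

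**Working it through.** **The plan's own figures.** 300 × 0.30 = 90 HPV-positive; 90 × 0.90 = 81 returning for colposcopy. With 24% against 49%, two-sided alpha 0.05, and 81 versus 81 treated as independent, power is 91.8%, so the claim of over 80% holds on that reading. None of these figures depends on a cytology cut-off.

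**Effect of one smear changing side.** Expected with high-grade disease: 81 × 0.24 = 19.44. Without: 81 − 19.44 = 61.56. One smear moves sensitivity by 1/19.44 = 5.1 points if the woman is diseased, or specificity by 1/61.56 = 1.6 points if she is not. For PPV at 49% with triage sensitivity s, TP = 19.44s and positives N = TP/0.49:

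- One added disease-free smear, TP/(N + 1): −2.0 points at s = 0.6; −1.2 at s = 1.0.
- One added diseased smear, (TP + 1)/(N + 1): +2.1 points at s = 0.6; +1.4 at s = 0.9.

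The two kinds pull PPV in opposite directions.

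**Worst case: every added smear is disease-free.** The test is an assumption (two-sided exact binomial against a fixed 24%); the protocol does not name it.

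| Start | p | Last significant | First not significant | Smears added |
|---|---|---|---|---|
| 12/24 | 0.006 | 12/29, p = 0.047 | 12/30, p = 0.052 | 6 |
| 16/33 | 0.003 | 16/43, p = 0.0495 | 16/44, p = 0.075 | 11 |
| 19/39 | 0.001 | 19/52, p = 0.049 | 19/53, p = 0.053 | 14 |

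That is 6 to 14 of 81 women (7% to 17%). The last row needs high-grade-only cytology to find all of about 19 diseased women, while B2 quotes cytology sensitivity of 43–94%.

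**Same test, with added smears diseased at the plan's own 24%** (diseased count rounded to the nearest whole number):

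- From 12/24: 21 added gives 17/45, p = 0.036. 22 added gives 17/46, p = 0.055, the first loss. 24 added gives 18/48, p = 0.041, significant again. 28 added gives 19/52, p = 0.049. 29 added gives 19/53, p = 0.053, and significance does not return. At 29 added, 0.24 × 29 = 7 diseased, which uses up all 19.
- From 16/33: only 19 − 16 = 3 diseased women remain, so about 12 smears can be added at that share (0.24 × 12 = 2.9). The result is 19/45, p = 0.008, and the conclusion does not change.

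**Pap against VIA on specificity** (exact McNemar, also assumed). This takes equal specificity at the start, and added Pap-positives who are disease-free and VIA-negative:

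- No discordant pairs at the start: 6 added, 0 v 6, p = 2 × (1/2)^6 = 0.031.
- 5 v 5 at the start: 10 added, 5 v 15, p = 0.041.
- 10 v 10 at the start: 12 added gives 10 v 22, p = 0.0501; 13 added gives 10 v 23, p = 0.035.

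The number needed depends on a starting disagreement that the protocol does not give.

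**The wordings side by side.** B2 is background. B3.A governs referral of HPV-negative women, about 300 − 90 = 210, and defers to the national guideline. B5 explains why HPV-positive women are all referred. None is offered as the Aim 1 threshold, and none makes persistence part of the accuracy analysis. HPV-positive women go to colposcopy whatever the smear shows, so the referral wording does not enter their accuracy table.

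**The case for a change.** The strongest reply is that an unstated cut-off is real analytic freedom. VIA is fixed as positive or negative, Pap is not, and low-grade smears are where a choice could be made after the histology is seen. The planned association between cytology and histopathology would show results by grade, but it does not say which two-by-two table is the Aim 1 result. If abnormal is only shorthand for the B5 wording, the rule would still rest on persistence, which the study does not observe.

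The omission stands as a description of the readable text, although the study-flow figure is not shown and may contain a cut-off. What does not stand is the step from omission to error. The 6-to-14 range puts every low-grade smear in a disease-free woman, in a group assumed to have 24% disease. It also ties the 49% target to the high-grade rule, which Sample Size does not do. If 49% belongs to any abnormality, dropping disease-free low-grade smears raises PPV and no positive finding is lost.

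**Conclusion.** No change to the plan follows. The protocol leaves a detail unstated that the analysis can supply. One smear allows any abnormality or high grade only, each estimate is correct for the algorithm it describes, and an analyst can name the cut-off and report both from the same 81 women. No rule that the protocol does state leads to a wrong result. It is good practice to record the choice before cytology is linked to histology, but the design, visits and sample size do not depend on it.

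The effect cannot be sized, because the number of low-grade smears is not given. From 12/24, 6 smears suffice in the worst case, while about 22 to 29 are needed at 24% diseased. From 16/33 at that share there is no reversal. These figures rest on assumed tests, assumed starting counts and 19 diseased women among 81.

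The differing referral wording in B2, B3.A and B5 for a single low-grade smear must be reconciled by the investigators. That is a matter of clinical text for about 210 HPV-negative women, and it affects no sensitivity, specificity or PPV calculated among HPV-positive women.
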